12. DATA REPORTING / REGULATORY REQUIREMENTS

Adverse event lists, guidelines, and instructions for AE reporting can be found in Section 7.0 (Adverse Events: List and Reporting Requirements).

12.1 **Data Reporting**

12.1.1 Method

This study will require data submission and reporting via the OnCore Database, which is the official database of the Markey Cancer Center Clinical Research Office (CRO). Instructions for submitting data are listed in Study-Specific Data Management Plans created by Data Management Specialist Senior housed in the Cancer Research Informatics (CRI) Shared Research Facility (SRF). **Please refer to the study calendar for all data reporting requirements.**

12.1.2 Responsibility for Data Submission

Study staff are responsible for submitting study data and/or data forms to OnCore as per the Markey Cancer Center CRO SOP's. This trial will be monitored by the MCC Data and Safety Monitoring Committee (DSMC) on a schedule determined by the Protocol Review and Monitoring Committee (PRMC) at the initial PRMC review. The CRO staff is responsible for compiling and submitting data for all participants and for providing the data to the Principal Investigator for review.

12.1.3 Responsibility for Data Monitoring

The MCC Quality Assurance Office will be responsible for creation and implementation of a clinical Data Monitoring Plan in collaboration with the PI and study team, as per QA Office SOPs.

13. STATISTICAL CONSIDERATIONS

13.1 Study Design/Endpoints

This is a 1:1 randomized, unblinded phase II trial of radiation with cisplatin weekly versus every three weeks for patients with locally advanced non-nasopharyngeal SCCHN. The primary endpoint is cisplatin-related acute toxicities (within the first 90 days after the start of radiation). These include all grade 3-5 events of nausea/vomiting, ototoxicity, nephrotoxicity, and neutropenia and thrombocytopenia. Secondary objectives include clinical outcomes (2-year local control rates, OS, PFS, response), additional toxicity outcomes (rates of dysphagia, dry mouth, and skin, other acute and late events according to CTCAE), correlates (oxidative stress markers), and quality of life outcomes (FACTHN, FACTCOG).

13.2 Sample Size/Accrual Rate

The primary objective of this study is to see if cisplatin delivered weekly results in fewer cisplatin-related toxicities and improved tolerability compared to cisplatin administered every 3 weeks. Both groups will still receive standard of care radiation therapy in addition to cisplatin. Assuming historical rates of 80% toxicities for patients receiving XRT + cisplatin every 3 weeks [10, 32-34], with 36 patients per arm we will have 80% power based on a Fisher's exact test to detect a decrease in toxicity rate to 50%, assuming a one-sided level of significance equal to 0.05. Conservatively assuming a 10% loss to follow-up, we will recruit 80 total patients for at least 72 analyzable.

Based on the Cancer Research Informatics SRF incidence tables for SCCHN from 2010-2014, **there were an average of 125 patients seen per year at MCC** that would be eligible for this trial based on tumor stage and tumor site. If even 33% of these subjects met all criteria and agreed to participate, we anticipate this study would be completed in 2 years. Our HN CCART has an excellent track record of accrual to clinical trials in this subset of SCCHN, thus we feel that this estimate is conservative and that it is possible that we could accrue faster than predicted.

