13.4 Analysis Plan

Following study completion, the percentage of subjects experiencing cisplatin-related actual toxicities in each group will be estimated along with exact 95% binomial confidence intervals. A Fisher's exact test will also be employed to test for differences between toxicity rates.

For all toxicity outcomes, incidence tables will be generated to summarize incidence of patients reporting at least one episode of each adverse event, incidence of adverse events causing withdrawals and incidence of serious adverse events. Listing of adverse events by patients will include the time to onset, the duration of each event, the severity of each event, and the relationship of the event to study therapy, whether it was a serious event, and whether it caused withdrawal.

All correlative and secondary endpoints are exploratory in nature and will be primarily descriptive; however, response and 2-year local control rates will be estimated with corresponding 95% confidence intervals and assessed for differences using Fisher's exact tests. PFS and OS will be displayed using Kaplan-Meier curves with estimated median times, and differences will be assessed using log rank tests. Repeated measures mixed models will be utilized to assess for differences in quality of life and correlative outcomes over time and between randomization groups.

In addition to those outlined above, subgroup analyses will also be run for each stratification cohort as numbers allow.

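### An optional improvement, not an error: Boschloo's exact test in place of Fisher's would hold the one-sided 5% level and raise power from 81% to 86% on the same 72 patients

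*Combined protocol and SAP*

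**What the plan says.** Section 13.1 describes the design: "This is a 1:1 randomized, unblinded phase II trial". The primary endpoint is grade 3-5 cisplatin-related acute toxicity within 90 days of the start of radiation.

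Section 13.2 sets the planning rates and the test. The control rate is given as "Assuming historical rates of 80% toxicities for patients receiving XRT + cisplatin every 3 weeks". The stated power is 80% at 36 per arm. The test behind that figure is Fisher's, described as an "exact test to detect a decrease in toxicity rate to 50%, assuming a one-sided level of significance equal to 0.05". For losses the section adds: "Conservatively assuming a 10% loss to follow-up, we will recruit 80 total patients for at least 72 analyzable".

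Section 13.4 puts estimation first, with exact 95% binomial intervals for each arm. It then says that a Fisher's "exact test will also be employed to test for differences between toxicity rates". It gives no side and no level. Section 13.5 plans no interim analysis, so the whole 5% is available at the end. Neither 13.2 nor 13.4 mentions that Fisher's test is conservative, or considers an unconditional exact test.

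**The concern.** Fisher's test conditions on the total number of patients with toxicity. In a two-arm randomised trial that total is random: the design fixes the arm sizes only. With small arms, few tables are possible for any given total, so the test usually cannot get close to its nominal level and part of the 5% goes unused.

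Boschloo's test takes the one-sided Fisher p-value as its statistic and finds the largest cutoff at which the rejection probability stays at or below 5% for every common toxicity rate. It is exact, and its rejection region contains Fisher's. At stake is about 5 points of power at the planned rates, available without enrolling anyone else.

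**Working it through.** **Inputs.** Control rate 0.80, alternative 0.50, one-sided level 0.05 and 36 analysable per arm (13.2); 1:1 allocation (13.1); no interim look (13.5). The comparison is unstratified, as 13.4 describes it.

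**Method.** Let *a* be the number with toxicity in the every-3-week arm and *b* the number in the weekly arm, each from 0 to 36, which gives 37 × 37 = 1,369 tables. The one-sided Fisher p-value is P(X ≥ *a*), where X is hypergeometric with 72 patients, *a* + *b* toxic and 36 in the arm. For a rejection region R,

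- power = Σ over R of Bin(*a*; 36, 0.80) × Bin(*b*; 36, 0.50);
- size at common rate π = Σ over R of Bin(*a*; 36, π) × Bin(*b*; 36, π), maximised over 2,000 values of π from 0.0005 to 0.9995.

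**Step 1: the plan's own figures.** With R = {Fisher p ≤ 0.05}, power is 80.9%, against 80% stated. Recruitment is 72 / 0.90 = 80, as stated. Both reproduce.

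**Step 2: Boschloo's cutoff.** The largest Fisher p-value that keeps the maximum size at or below 0.05 is 0.0718. The maximum size is then 4.82%. The next attainable p-value, 0.0744, would give 5.11%. The region is Fisher's plus 18 further tables.

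**Step 3: true size, like for like.**

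| Common rate | Fisher | Boschloo |
|---|---|---|
| 0.50 | 3.82% | 3.95% |
| 0.60 | 3.53% | 4.48% |
| 0.65 | 3.21% | 4.81% |
| 0.70 | 2.94% | 4.66% |
| 0.80 | 2.70% | 4.04% |
| 0.90 | 1.69% | 3.05% |
| Maximum over all rates | 3.82% | 4.82% |

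**Step 4: power at 36 per arm.**

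| True rates | Fisher | Boschloo | Gain (points) |
|---|---|---|---|
| 80% v 50% (planned) | 80.9% | 85.8% | 4.9 |
| 80% v 55% | 66.4% | 73.8% | 7.4 |
| 70% v 40% | 79.5% | 80.5% | 1.0 |

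**Step 5: what the gain is worth.** Fisher's test needs 42 per arm for 85.8% power (41 gives 84.8%). That is 84 analysable patients, 12 more than planned, or 84 / 0.90 = 93.3, so 94 recruited rather than 80. If only 34 per arm were analysable, Fisher's power would be 77.3% and Boschloo's 83.8%.

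**Step 6: an example.** For 29/36 v 22/36, the one-sided Fisher p is 0.059 and the one-sided Boschloo p is 0.038. This is one of the 18 extra tables.

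**Step 7: dependence on the side.** All of this uses the one-sided 0.05 of 13.2. A two-sided 0.05 Fisher test at 36 per arm has 69.6% power.

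**The case against.** The strongest reply is that nothing here is wrong. The plan names a valid test, sizes the trial for that test and meets its 80% target, so the conservatism is already paid for in the 36 per arm. Conditional against unconditional exact testing is a long-standing choice between valid methods. This stands, and it is why the point is an improvement and not a defect. It does not remove the case for a test that never has less power here, holds the same level and needs no extra patients.

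Other replies also stand, as limits:

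- A reader might infer that the lost power matters because the sample size cannot easily be raised. Section 13.2 points the other way: it counts 125 potentially eligible patients a year, expects to finish in 2 years and thinks accrual could be faster.
- A reader might take this to be the trial's only confirmatory test. Section 13.4 calls the secondary and correlative endpoints exploratory, but never calls the primary test confirmatory.
- The gain rests on a one-sided level that 13.4 does not repeat. Stating the side matters more than the choice of test: 80.9% against 69.6% for Fisher's test alone.
- Randomisation is stratified by cohort (13.3), and neither test uses the strata.
- The trial is unblinded, and 13.6 gives the statistician scheduled access to data. The documents do not show whether outcomes had accrued. Switching after seeing results by arm would not be sound, and reporting two p-values without saying which decides would invite selection in the 18 tables where they disagree.

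**Conclusion.** The point holds as a low-cost, optional improvement. At 36 per arm and one-sided 0.05, Fisher's true type I error is 2.7% to 3.8% for common rates of 0.50 to 0.80, and lower still at, for example, 0.90. Boschloo's is about 3.9% to 4.8% over the same range. Power at the planned rates rises by 4.9 points. The gain varies with the true rates, but cannot be negative because Boschloo's region contains Fisher's.

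It would be tempting to conclude that the trial is underpowered or its test invalid. The documents do not support that: the stated power reproduces and the level is held.

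The figures assume exactly 36 analysable patients per arm, an unstratified comparison, one-sided testing at 0.05, and a choice of test fixed before any outcome data by arm are seen.

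**What to change.** - **Section 13.4:** name Boschloo's exact unconditional test, one-sided at 0.05, as the single primary test of the toxicity rates. Report Fisher's p-value beside it as supportive only, and say that it does not enter the decision.
- **Section 13.2:** state that 36 per arm gives about 86% power with this test, and 81% with Fisher's, at 80% v 50%. The sample size stays as it is.
- **Amendment record:** state that the change was made before any outcome data by arm were seen. If that cannot be stated, keep Fisher's test as primary.

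If the team prefers Fisher's test in any case, 13.4 should still state the one-sided 0.05 level used in 13.2.

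The cost is a few sentences in two sections. The downside is a test that fewer readers know, although standard software provides it.

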13.3 Stratification Factors

13.3.1 Randomization will be stratified by type of SCCHN: Cohort (1) is unresectable and Cohort (2) is resected and at high risk of recurrence as defined by the presence of one of the following criteria:

- extracapsular nodal extension
- invasive cancer at the primary tumor resection margin (positive margin)
- lymphovascular invasion
- perineural invasion
- pT3 or pT4 primary
- presence of multilevel nodal disease

13.4 Analysis Plan

Following study completion, the percentage of subjects experiencing cisplatin-related actual toxicities in each group will be estimated along with exact 95% binomial confidence intervals. A Fisher's exact test will also be employed to test for differences between toxicity rates.

For all toxicity outcomes, incidence tables will be generated to summarize incidence of patients reporting at least one episode of each adverse event, incidence of adverse events causing withdrawals and incidence of serious adverse events. Listing of adverse events by patients will include the time to onset, the duration of each event, the severity of each event, and the relationship of the event to study therapy, whether it was a serious event, and whether it caused withdrawal.

All correlative and secondary endpoints are exploratory in nature and will be primarily descriptive; however, response and 2-year local control rates will be estimated with corresponding 95% confidence intervals and assessed for differences using Fisher's exact tests. PFS and OS will be displayed using Kaplan-Meier curves with estimated median times, and differences will be assessed using log rank tests. Repeated measures mixed models will be utilized to assess for differences in quality of life and correlative outcomes over time and between randomization groups.

In addition to those outlined above, subgroup analyses will also be run for each stratification cohort as numbers allow.

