1.2 Secondary Objectives

1.2.1 To compare the following therapeutic endpoints in both populations:

- 2-year local control rates
- Overall survival (OS)
- Progression free survival (PFS)
- Response Rate (Cohort 1 only, as Cohort 2 is completely resected)

1.2.2 To compare and contrast the development of oxidative stress markers which occur as a result of exposure to weekly or every 3-week doses of cisplatin in this population

1.2.3 Rates of radiation related CTCAE adverse events, specifically: mucositis, dysphagia, dry mouth, and skin and their relationships with patient reported outcomes at 3 months and 12 months

1.2.4 CTCAE acute (< 90 days from start of chemoradiation) adverse events related (possibly, probably or definitely) to cisplatin or radiation

- 1.2.5 CTCAE late (> 90 days from start of chemoradiation) adverse events related (possibly, probably or definitely) to cisplatin or radiation.
- 1.2.6 Quality of life as measured by Functional Assessment of Cancer Therapy-Head & Neck (FACTHN) and Functional Assessment of Cancer Therapy Cognition (FACTCOG) at baseline, 3, and 12 months from end of RT

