5.5 Duration of Therapy

In the absence of treatment delays due to adverse event(s), treatment will continue for 7 weeks or until one of the following criteria applies:

- Disease progression,
- Intercurrent illness that prevents further administration of treatment,
- Unacceptable adverse event(s),
- Patient decides to withdraw from the study, or
- General or specific changes in the patient's condition render the patient unacceptable for further treatment in the judgment of the investigator.

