5.6 Duration of Follow Up

Patients will be followed for 2 years after completion of chemoradiation or until death, whichever occurs first, for toxicity and PFS. Following resolution of toxicity and completion of primary endpoint assessment by PI and study team, long-term follow-up of 5 years will be performed by the Kentucky Cancer Registry. Patients removed from study for unacceptable adverse event(s) will be followed until resolution or stabilization of the adverse event.

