5.7 Criteria for Removal from Study

Patients will be removed from study when any of the criteria listed in Section 5.5 applies. The reason for study removal and the date the patient is removed must be documented in the Case Report Form.

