10. STUDY CALENDAR

Baseline evaluations are to be conducted as follows:

- Within 3 weeks prior to registration: Complete history, physical examination, and evaluation of ECOG Performance Status, CBC; serum chemistry tests to include alkaline phosphatase, creatinine, electrolytes, AST (SGOT), and total bilirubin.
- All radiographic studies should be completed within:
 - Cohort 1: 6 weeks prior to registration
 - Cohort 2: 8 weeks prior to registration
- In the event that the patient's condition is deteriorating, laboratory evaluations should be repeated within 48 hours prior to initiation of the next cycle of therapy.

Pre-Study	Wk 1	Wk 2	Wk 3	Wk 4	Wk 5	Wk 6	Wk 7	Post Treatment Follow up	Long term Follow up ^b
Cisplatin Arm 1	A			A			A		
Cisplatin Arm 2	B	B	B	B	B	B	B		
Informed consent	X								
Demographics, medical history	X								
Concurrent meds		X ⁱ							
Physical exam	X	X		X			X	X	X ^h
Pulse, blood pressure	X	X		X			X	X	
Height	X								
Weight ^a	X	X	X ^a	X ^a	X	X ^a	X ^a	X	
Performance status	X	X						X	
CBC w/diff, plts ^a	X	X	X ^a	X ^a	X	X ^a	X ^a	X	X
Serum basic chemistry ^b			X ^a	X ^a		X ^a	X ^a		
Serum comprehensive chemistry ^c	X	X		X			X	X	
Adverse event evaluation		X-----							X
Tumor measurements	X ^d							X ^e	X ^e
B-HCG	X ^f								
Correlative studies		X							
FACTHN and FACT-COG ^g	X ^g						X ^g	X ^g	

A: Arm 1: Cisplatin 100 mg/m² every 3 weeks for 3 total doses

B: Arm 2: Cisplatin 40 mg/m² every week for 7 total doses

a: Every 3 weeks for Arm 1 during radiation, weekly for Arm 2 during radiation, and then as scheduled.

b: Weeks 2,3,5, 6 of Arm 2 only: creatinine, glucose, potassium, sodium.

c: Every three weeks for both arms: Albumin, alkaline phosphatase, total bilirubin, calcium, creatinine, potassium, SGOT [AST], SGPT [ALT], sodium.

- d: Baseline scans can include either: 1) CT with contrast or MRI of the head and neck region, CT of chest or chest x-ray. Response assessment should include assessment of all sites of disease and use the same imaging method as was used at baseline.
- e: Restaging scans must be repeated after the end of protocol treatment within 8 weeks of completion of radiation. Thereafter, scans of the head and neck will be repeated as clinically indicated, but at a minimum of every 6 months (± 6 weeks) for the first two years. Following this, all scans are at the treating physician's discretion.
- f: Serum pregnancy test (women of childbearing potential).

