11.1.6 Progression-Free Survival

PFS is defined as the duration of time from start of treatment to time of progression or death, whichever occurs first.

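### Two-year local control, an exploratory endpoint, is tested as a simple proportion although patients can be lost before 2 years; a censoring-based 2-year estimate is the better method

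*Combined protocol and SAP*

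**What the plan says.** Local control is named in Sections 1.2.1, 2.5, 13.1 and 13.4 and defined in none of them. Section 13.4 classes all secondary endpoints as exploratory and mainly descriptive, then commits to a rate and a test: "response and 2-year local control rates will be estimated with corresponding 95% confidence intervals and assessed for differences using" Fisher's exact tests. PFS and OS are given Kaplan-Meier curves and log rank tests.

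Only PFS has a definition and a time origin (Section 11.1.6): "PFS is defined as the duration of time from start of treatment to time of progression or death, whichever occurs first".

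Section 13.2 makes an allowance for loss when sizing the trial for its 90-day primary endpoint: "Conservatively assuming a 10% loss to follow-up, we will recruit 80 total patients for at least 72 analyzable".

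The two cohorts start from different disease states. Section 1.2.1 limits one endpoint accordingly: "Response Rate (Cohort 1 only, as Cohort 2 is completely resected". Local control is to be compared in both cohorts.

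Section 2.5 states the local control hypothesis at 1 year; the endpoint in 1.2.1, 13.1 and 13.4 is at 2 years.

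**The concern.** Fisher's exact test needs a yes/no status at 2 years for every patient counted. A patient last seen free of local failure at, say, 14 months has no such status. The analyst must exclude that patient, call the outcome controlled, or call it failed. The plan does not choose, and the trial is unblinded, so the choice could be made with the data in view.

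At stake are the per-arm 2-year rate and its confidence interval. Section 2.5 makes comparable local control half of the overall hypothesis, so readers will look at this figure even though it is exploratory. Estimators that use each patient's follow-up up to the point of loss avoid the choice, and the plan already uses them for PFS and OS.

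**Working it through.** **The plan's own figures.** Section 13.2: 72 / (1 − 0.10) = 80, as stated. That figure concerns the primary endpoint. The plan gives no figure for local control, so the inputs below are assumptions.

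**Assumed inputs.** By 2 years, 25% have local failure and 15% die without it, so 75% are truly free of local failure when death is not counted as one. Hazards are constant. Loss is independent of outcome, with 10% or 20% of patients lost event-free before 2 years.

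**Hazards.** Total event hazard = −ln(0.60)/2 = 0.2554 per year. Local failure: 0.2554 × 25/40 = 0.1596. Death without it: 0.2554 × 15/40 = 0.0958.

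**Cells.** With loss hazard c and h = 0.2554 + c, the event-free share is exp(−2h), and each other cell is (its hazard / h) × (1 − exp(−2h)). Setting the lost cell to 10% gives c = 0.0679; setting it to 20% gives c = 0.1454.

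| Loss | Event-free | Local failure | Death first | Lost |
|---|---|---|---|---|
| 10% | 0.5238 | 0.2351 | 0.1411 | 0.100 |
| 20% | 0.4486 | 0.2196 | 0.1318 | 0.200 |

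**Expected rate free of local failure (truth 75%).**

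| Rule for lost patients | 10% loss | 20% loss |
|---|---|---|
| Controlled | 0.5238 + 0.1411 + 0.100 = 76.5% | 0.4486 + 0.1318 + 0.200 = 78.0% |
| Excluded | 0.6649 / 0.9 = 73.9% | 0.5804 / 0.8 = 72.6% |
| Failure | 66.5% | 58.0% |

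At 10% loss the biases are about +1.5, −1.1 and −8.5 points. None of the three rules recovers 75%.

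**Other inputs.** Take independent exponential times with 2-year net risks of 20% for local failure and 20% for death, so the truth is 82.0%. The three rules, in the same order, give 82.4%, 81.7% and 78.4% at 5% net loss; 82.8%, 81.3% and 74.8% at 10%; and 83.7%, 80.6% and 67.5% at 20%. The pattern is the same.

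**Between arms, identical truth.** Equal loss gives equal expected rates, hence no bias. In simulation (40 per arm, two-sided 0.05) Fisher's test then rejects in 2.8–3.5% of trials under every rule. With 10% against 20% loss, which is a further assumption, the false differences are 76.49 − 78.04 = −1.55, 73.88 − 72.55 = +1.33 and 66.49 − 58.04 = +8.45 points; Fisher's test rejects in 3.1%, 3.7% and 8.2%.

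**The alternative.** The Aalen-Johansen estimate of cumulative incidence, simulated with 10% against 20% independent loss, averages 75.0% free of local failure in both arms, with a mean difference of 0.00 points (Monte Carlo SE 0.07).

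**Precision.** With 10% loss in both arms the SD of the difference is 0.100, so the 95% half-width is 1.96 × 0.100 = 0.196, about 20 points.

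**The case against.** The strongest case is that this is a small matter. The endpoint is exploratory. Excluding lost patients, which is what many analysts would do by default, costs about 1 point against a confidence interval of ±20. The 10-point spread between the extreme rules (76.5% to 66.5%) simply restates the assumed 10% loss. All of this stands, and it limits the weight of the point. It does not favour the proportion, because the alternative is cheap and removes the bias when loss is independent.

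Section 13.7.2 counts unknown outcomes as failures. That rule is written for response, which Section 3.1.3 says is not assessed in Cohort 2, so it does not settle local control. If borrowed, it is the rule with the largest bias above.

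Four stronger readings are tempting and not supported:

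- *The arms will be compared unfairly.* This needs unequal loss, and nothing in the documents establishes it. Larger swings can be constructed by varying deaths and losses by arm and by also counting death as failure, but the latter is a different endpoint, alive with local control.
- *Ten percent will be lost by 2 years.* Section 13.2 does not say so. Its allowance is for analyzable patients and may include some who are never evaluable. Nor does Section 5.7 ("Patients will be removed from study when any of the criteria listed in Section 5.5 applies") show that disease assessment ends at removal.
- *The follow-up clocks conflict.* Section 5.6 says "Patients will be followed for 2 years after completion of chemoradiation or until death, whichever occurs first, for toxicity and PFS". That is a duration of follow-up, not an endpoint origin, and 2 years from start of treatment falls inside it.
- *Scans stop too early.* The calendar requires head and neck scans at least six-monthly, within 6 weeks either side, "for the first two years. Following this, all scans are at the treating" physician's discretion. The anchor is not stated. If it is completion of radiation, the last window opens at about week 104 − 6 = 98 after completion. With 6–7 weeks of radiation, that is week 104–105 from start. An earlier anchor would bring some censoring forward but would contradict nothing.

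Counting a death without local failure as controlled is also not an error in itself: with no loss, that proportion equals one minus the cumulative incidence.

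**Conclusion.** The concern holds as a choice-of-method point on an exploratory secondary endpoint. A simple proportion needs a rule for patients lost event-free, the plan has none, and each available rule misstates the per-arm rate. The size depends on assumed event rates and loss: at 10% independent loss the bias is 1 to 2 points if lost patients count as controlled or are excluded, and about 8.5 points if they count as failures. It would vanish only if no patient were lost event-free before 2 years. The case does not rest on between-arm bias, and the primary analysis, its power and the sample size are untouched. The missing definition and time origin matter because neither the present analysis nor a better one can be carried out without them.

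**What to change.** In Section 13.4, for local control only (Fisher's test can stay for response):

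- Replace the proportion and Fisher's test with the 2-year cumulative incidence of local failure by assigned arm. Treat death without local failure as a competing event, and censor patients without an event at their last disease assessment. Report the between-arm difference at 2 years with its 95% CI.
- State one time origin that exists for every patient analysed: start of treatment, as for PFS, if the set is treated patients; randomisation if all randomised patients are included.
- Define local failure to cover persistent disease in Cohort 1, dated at the assessment that shows it; recurrence after complete response in Cohort 1; and recurrence in Cohort 2. Say whether regional failure counts.
- Tabulate losses by arm.
- Reconcile the 1-year time point in Section 2.5 with the 2-year endpoint.

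The cost is wording and slightly more analysis work; the scheduled scans supply the data. Two limits remain. Censoring is still assumed independent of outcome, which is why losses should be shown by arm. The 95% CI for the difference stays at about ±20 points, so the result will not establish comparable local control under any method.

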5.2.1 Planned Treatment

Treatment will consist of standard of care radiation therapy to the primary tumor of the head and neck and involved nodal metastasis and draining nodal basin, as determined by treating radiation oncologist. Patients will be randomized to receive cisplatin at 100 mg/m² every 3 weeks (3 doses) during radiation versus cisplatin at 40 mg/m² once weekly (7 doses) during radiation. This will provide similar cumulative doses of cisplatin in all arms of the study.

Cisplatin Arm	Maximum Cumulative Dose
Every 3 weeks	300 mg/m ²
Weekly	280 mg/m ²

According to a recent review, total doses above 200 mg/m² during radiation lead to higher overall survival [17], and every attempt will be made to reach at least 200 mg/m². Because of the significant differences in response to therapy in oropharyngeal carcinoma (OPC) due to human papilloma virus (HPV) infection, HPV status will be recorded at baseline and adjusted during final analyses where appropriate.

Patients will first be designated by the enrolling CRA, in conjunction with the enrolling physician, as either: a) Cohort 1 (locally advanced non-nasopharyngeal SCCHN that is unresectable) OR b) Cohort 2 (resected and at high risk of recurrence with at least one of the following criteria: extracapsular nodal extension, or invasive cancer at the primary tumor resection margin (positive margin), lymphovascular invasion or perineural invasion, pT3 or pT4 primary, or the presence of multilevel nodal disease. Subjects will then be randomized to receive either Arm 1 or Arm 2 cisplatin as below.

Radiation and Cisplatin will be given concurrently and should start on the same day, \pm 1 day. Radiation will continue without interruption whenever possible. Radiation delays or interruptions will be the decision of the treating radiation oncologist, as outlined in section 5.3.

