- g: Pre-study, at 3 months (± 6 weeks) and 12 months (± 12 weeks) following initiation of treatment.
- h: Physical exams will be repeated as clinically indicated, but at a minimum of every 6 months (± 6 weeks) for the first two years. Following this, all follow-up is at the treating physician's discretion.
- i: Only on Days 1 and 2 of cycle 1

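### The quality-of-life mixed model makes no provision for using the baseline FACT score; adjusting for it would sharpen the arm comparison at no cost

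*Combined protocol and SAP*

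**What the plan says.** Section 13.4 (Analysis Plan) gives quality of life one sentence: "Repeated measures mixed models will be utilized to assess for differences in quality of life and correlative outcomes over time and between randomization groups". It lists no fixed effects, covariates, arm-by-visit term or covariance structure, and does not say which contrast is the between-arm result. The same section sets the status of the endpoint: "All correlative and secondary endpoints are exploratory in nature and will be primarily descriptive".

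Item 1.2.6 in section 1.2 schedules the FACT instruments "at baseline, 3, and 12 months from end of RT". Footnote g of the study calendar (section 10) has "Pre-study, at 3 months (± 6 weeks) and 12 months (± 12 weeks) following initiation of treatment". On either version there is one score before treatment and two after it.

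The only covariate adjustment mentioned anywhere is in section 5.2.1: "HPV status will be recorded at baseline and adjusted during final analyses where appropriate". Section 13.3 stratifies randomisation by cohort (unresectable or resected). The baseline FACT score is not named as a covariate in any section.

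**The concern.** Before treatment, randomised arms differ only by chance. A baseline score can therefore serve the arm comparison in one useful way: by removing between-patient variation from the later scores. The sentence in section 13.4 does not arrange for that, and its two ordinary readings each give something up.

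- **Arm-by-time term with a separate baseline mean per arm.** The arm comparison is then a difference in change from baseline. It is unbiased, but it carries the full noise of the baseline measurement.
- **Arm effect over all visits.** This averages in a visit at which no treatment effect can exist, so the estimate shrinks.

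The sample size was set for a binary toxicity endpoint, and section 2.4 says the cognitive instrument is there to pick up subtle changes. Precision on these scores is worth having when the data that supply it are already collected. In an open-label trial it also helps to fix the contrast before scores by arm have been seen.

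**Working it through.** **The plan's own figure.** The documents give no SD, effect size, correlation or power for FACT, so there is no quality-of-life figure to reproduce. The 36 per arm used below comes from the primary design in section 13.2 (toxicity 80% versus 50%, Fisher's exact test, one-sided 0.05). Exact enumeration gives 80.9% power at 36 per arm against the stated 80%, and 72/(1 − 0.10) = 80 recruited, as stated. That calculation is sound and is not affected by this point.

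**Assumptions (not in the documents).** Score SD 1 at every visit; the same correlation ρ between any two of baseline, 3 and 12 months; no true difference at baseline and an equal difference at 3 and 12 months; no missing data; n = 36 per arm; normal approximation.

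**Contrasts.** Weights apply to (baseline, 3 months, 12 months). The per-patient variance v gives SE = √(2v/n).

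- Arm effect over three visits, (1/3, 1/3, 1/3): v = (1 + 2ρ)/3. Expected value is (0 + 1 + 1)/3 = 2/3 of the effect.
- Change from baseline, (−1, 1/2, 1/2): v = 1.5(1 − ρ). Expected value is the full effect.
- Baseline-adjusted, (−ρ, 1/2, 1/2): v = (1 − ρ)(1 + 2ρ)/2. Expected value is the full effect.

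The change-to-adjusted variance ratio is 1.5(1 − ρ) ÷ [(1 − ρ)(1 + 2ρ)/2] = 3/(1 + 2ρ). It does not depend on n.

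| ρ | v, three-visit | v, change | v, adjusted | change/adjusted |
|---|---|---|---|---|
| 0.4 | 0.600 | 0.900 | 0.540 | 1.67 |
| 0.5 | 0.667 | 0.750 | 0.500 | 1.50 |
| 0.7 | 0.800 | 0.450 | 0.360 | 1.25 |

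**Expected z per 1 SD effect at ρ = 0.5.**

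- Three-visit: 0.667/√(2 × 0.667/36) = 0.667/0.192 = 3.46
- Change: 1/√(2 × 0.75/36) = 1/0.204 = 4.90
- Adjusted: 1/√(2 × 0.50/36) = 1/0.167 = 6.00

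At ρ = 0.5 the change contrast would need 36 × 1.5 = 54 per arm to match the adjusted one at 36.

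**In terms of power.** For an assumed true difference of 0.5 SD and two-sided 0.05, at ρ = 0.3 / 0.5 / 0.7:

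- adjusted: 81% / 85% / 94%
- change: 54% / 69% / 89%
- three-visit: 49% / 41% / 35%, with an expected estimate of 0.33 SD instead of 0.50

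**Baseline as an outcome.** Keeping baseline as a visit in the model but constraining the arm means to be equal there gives the same precision as using it as a covariate. A 2,000-run simulation at ρ = 0.5, with the covariance treated as known, gave a mean estimate of 0.50 and an SE of 0.163, against 0.167 from the formula.

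**Visit timing.** Section 5.3.1 delivers radiation over 6–7 weeks. Taking 3 months as 13 weeks, a visit 3 months after the end of radiation falls at 13 + 6 to 13 + 7 = 19–20 weeks from the start. The calendar window counted from the start is 13 ± 6 = 7–19 weeks. The first post-treatment visit aimed at by section 1.2 therefore sits at or beyond the edge of the window in section 10.

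**The case against.** The strongest reply is that section 13.4 does not describe the faulty model. It neither plans nor excludes baseline adjustment, and because HPV adjustment appears only in section 5.2.1, the sentence in 13.4 is clearly not a full covariate list. A statistician could fit a baseline-adjusted model and remain within the plan. This stands: a reader might infer that the trial has decided to treat baseline as just another time point and leave it unadjusted, but the documents say neither.

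A reader might also infer that the planned estimate is diluted by a third. That follows only if the arm effect is averaged over all three visits. The wording fits an arm-by-time model at least as well, and that model dilutes nothing. Nor is having baseline among the outcomes a defect in itself, as the constrained model shows.

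The endpoint is exploratory and mainly descriptive, and no error rate or decision rests on it. The correlation and effect pattern are assumed, and 36 per arm is the number for a 90-day endpoint, so fewer patients will have 12-month scores. These points limit how much the matter weighs. They do not remove it: section 13.4 still commits to a between-arm model, the efficient forms have to be chosen deliberately, and adjustment was the most precise unbiased option at every correlation tried.

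**Conclusion.** The point holds as a low-severity, free improvement. The plan collects a baseline FACT score and does not provide for its use in the arm comparison. With equally correlated visits, an equal effect at both later visits and complete data, a change contrast has 1.25 to 1.67 times the variance of a baseline-adjusted contrast for correlations from 0.7 down to 0.4, and 1.5 times at 0.5. Shrinkage to two thirds is a risk under one permissible reading, not a property of the plan. The variance ratio does not depend on the number per arm; the z values and powers do, and they are optimistic if scores are missing at 12 months. The primary toxicity test and sample size are unaffected.

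**What to change.** Add to section 13.4, in words such as:

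> FACT scores at 3 and 12 months will be analysed in a mixed model with arm, visit, arm-by-visit interaction, cohort (the randomisation stratum) and the baseline score as covariate. Equivalently, baseline may be kept as an outcome with the arm means constrained equal at that visit. The arm difference and its 95% CI will be reported at each visit.

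State the covariance structure in the same place.

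In the same edit, reconcile sections 1.2 and 10 on whether the visits are counted from the end of radiation or from the start of treatment, since the model's visits cannot be defined until that is settled.

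Extend the approach to the serum markers only if a pre-dose sample is drawn. Section 9.2 leaves collection to a Lab Manual that is not among the documents, so this cannot be confirmed here.

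The cost is a short addition to the analysis plan and one timing correction, best made before FACT scores by arm are examined. It needs no new data and no extra patients.
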